1 OVERVIEW

Study Title: Improving Asthma Care Together (IMPACT): A Pilot RCT

1.1 Home institution. Identify the institution through which the lead researcher listed on the IRB application will conduct the research. Provide any helpful explanatory information.

In general, the home institution is the institution (1) that provides the researcher's paycheck and that considers him/her to be a paid employee, or (2) at which the researcher is a matriculated student. Scholars, faculty, fellows, and students who are visiting the UW and who are the lead researcher: identify your home institution and describe the purpose and duration of your UW visit, as well as the UW department/center with which you are affiliated while at the UW.

Note that many UW clinical faculty members are paid employees of non-UW institutions.

The UW IRB provides IRB review and oversight for only those researchers who meet the criteria described in the [SOP Use of the UW IRB](#).

University of Washington School of Nursing

1.2 Consultation history. Has there been any consultation with someone at HSD about this study?

It is not necessary to obtain advance consultation. However, if advance consultation was obtained, answering this question will help ensure that the IRB is aware of and considers the advice and guidance provided in that consultation.

X	No
	Yes

→ If yes, briefly describe the consultation: approximate date, with whom, and method (e.g., by email, phone call, in-person meeting).

1.3 Similar and/or related studies. Are there any related IRB applications that provide context for the proposed activities?

Examples of studies for which there is likely to be a related IRB application: Using samples or data collected by another study; recruiting subjects from a registry established by a colleague's research activity; conducting Phase 2 of a multi-part project, or conducting a continuation of another study; serving as the data coordinating center for a multi-site study that includes a UW site.

Providing this information (if relevant) may significantly improve the efficiency and consistency of the IRB's review.

X	No
	Yes

→ If yes, briefly describe the other studies or applications and how they relate to the proposed activities. If the other applications were reviewed by the UW IRB, please also provide: the UW IRB number, the study title, and the lead researcher's name.

The IMPACT intervention has been developed in collaboration with participants under UW IRB: STUDY00003144: Improving Asthma Care Together (IMPACT): A Usability and Acceptability Study (short title - IMPACT Study). PI [name]. This protocol proposes to test the IMPACT intervention in an RCT.

1.4 Externally-imposed urgency or time deadlines. Are there any externally-imposed deadlines or urgency that affect the proposed activity?

HSD recognizes that everyone would like their IRB applications to be reviewed as quickly as possible. To ensure fairness, it is HSD policy to review applications in the order in which they are received. However, HSD will assign a higher priority to research with externally-imposed urgency that is beyond the control of the researcher. Researchers are encouraged to communicate as soon as possible with their HSD staff contact person when there is an urgent situation (in other words, before submitting the IRB application). Examples: a researcher plans to test an experimental vaccine that has just been developed for a newly emerging epidemic; a researcher has an unexpected opportunity to collect data from students when the end of the school year is only four weeks away.

HSD may ask for documentation of the externally-imposed urgency. A higher priority should not be requested to compensate for a researcher's failure to prepare an IRB application in a timely manner. Note that IRB review requires a certain minimum amount of time; without sufficient time, the IRB may not be able to review and approve an application by a deadline.

No

Yes → If yes, briefly describe the urgency or deadline as well as the reason for it.

1.5 Objectives Using lay language, describe the purpose, specific aims, or objectives that will be met by this specific project. If hypotheses are being tested, describe them. You will be asked to describe the specific procedures in a later section.

If this application involves the use of a HUD “humanitarian” device: describe whether the use is for “on-label” clinical patient care, “off-label” clinical patient care, and/or research (collecting safety and/or effectiveness data).

The purpose of this project is to pilot test the **IMPACT** mHealth application with a sample of sixty children (7-11 years) with persistent asthma and one of their parents.

The specific aims are to:

1. Determine the feasibility, acceptability and initial efficacy of IMPACT with 60 parent-child dyads in an eight-week pilot randomized controlled trial (RCT).

- a. We will use a priori benchmarks to determine the feasibility of IMPACT based on study eligibility, enrollment, and retention.
- b. Acceptability of IMPACT features and engagement will be determined via exit surveys and semi-structured interviews.
- c. Preliminary effect sizes compared to control will be reported on primary outcomes (asthma responsibility, self-efficacy) and secondary outcomes (medication adherence, asthma control and quality of life).
- d. We will also conduct preliminary testing of dyadic interdependence of asthma responsibility over time.

1.6 Study design. Provide a one-sentence description of the general study design and/or type of methodology.

Your answer will help HSD in assigning applications to reviewers and in managing workload. Examples: a longitudinal observational study; a double-blind, placebo-controlled randomized study; ethnographic interviews; web scraping from a convenience sample of blogs; medical record review; coordinating center for a multi-site study.

This study will use a randomized controlled trial design with two parallel study arms, intervention and control (usual care)

1.7 Intent. Check all the descriptors that apply to your activity. You must place an "X" in at least one box.

This question is essential for ensuring that your application is correctly reviewed. Please read each option carefully.

Descriptor
 1. Class project or other activity whose purpose is to provide an educational experience for the researcher (for example, to learn about the process or methods of doing research).
 2. Part of an institution, organization, or program's own internal operational monitoring.
 3. Improve the quality of service provided by a specific institution, organization, or program.
 4. Designed to expand the knowledge base of a scientific discipline or other scholarly field of study, and produce results that: 
• Are expected to be applicable to a larger population beyond the site of data collection or the specific subjects studied, or• Are intended to be used to develop, test, or support theories, principles, and statements of relationships, or to inform policy beyond the study.
 5. Focus directly on the specific individuals about whom the information or biospecimens are collected through oral history, journalism, biography, or historical scholarship activities, to provide an accurate and evidence-based portrayal of the individuals.
 6. A quality improvement or program improvement activity conducted to improve the implementation (delivery or quality) of an accepted practice, or to collect data about the implementation of the practice for clinical, practical, or administrative purposes. This does not include the evaluation of the efficacy of different accepted practices, or a comparison of their efficacy.
 7. Public health surveillance activities conducted, requested, or authorized by a public health authority for the sole purpose of identifying or investigating potential public health signals or timely awareness and priority setting during a situation that threatens public health.
 8. Preliminary, exploratory, or research development activities (such as pilot and feasibility studies, or reliability/validation testing of a questionnaire)
 9. Expanded access use of a drug or device not yet approved for this purpose
 10. Use of a Humanitarian Use Device
 11. Other. Explain: 

1.8 Background, experience, and preliminary work. Answer this question only if the proposed activity has one or more of the following characteristics. The purpose of this question is to provide the IRB with information that is relevant to its risk/benefit analysis.

- Involves more than minimal risk (physical or non-physical)
- Is a clinical trial, or
- Involves having the subjects use a drug, biological, botanical, nutritional supplement, or medical device.

"Minimal risk" means that the probability and magnitude of harm or discomfort anticipated in the research are not greater than those ordinarily encountered in daily life or during the performance of routine physical or psychological examinations or tests.

a. Background. Provide the rationale and the scientific or scholarly background for the proposed activity, based on existing literature (or clinical knowledge). Describe the gaps in current knowledge that the project is intended to address.

This should be a plain language description. Do not provide scholarly citations. Limit your answer to less than one page, or refer to an attached document with background information that is no more than three pages long.

This is a minimal risk study that involves a clinical trial.

Asthma is most common chronic condition of childhood, affecting over six million US children. Asthma is an incurable, lifelong condition that places children at increased risk for functional impairments, decreased quality of life, school absences, increased healthcare utilization, and irreversible structural airway remodeling. Asthma management involves symptom monitoring and response, trigger avoidance, and timely and appropriate medication use. Unfortunately, fewer than 50% of children with asthma are adherent to asthma management regimens, leading to increased disease morbidity and mortality and potentially irreversible airway damage. Improving pediatric asthma management represents a critical health need.

Children with asthma are missing a voice in their own care. The school-age years (7-11) represent a natural transition in asthma management, as children must assume some responsibility for asthma-related care while they spend increasing time away from parents at school and other extracurricular activities. Developmentally, school-age children are rule-driven, understand right and wrong, and are able to problem solve, which supports their capability to be active participants in their own asthma management. Yet, existing interventions focus on parents alone and use prescriptive approaches, telling the parent what to "do" to the child to manage their asthma. As a result, our current strategies are failing to provide children with asthma and their families the tools they need to manage asthma successfully within the realities of their daily lives. The answer to this problem lies in shared asthma management by the parent-child dyad, with the school-age years (7-11) the ideal developmental period for children to begin sharing responsibility with their parents and establishing lifelong health behaviors.

b. Experience and preliminary work. Briefly describe experience or preliminary work or data (if any) that you, your team, or your collaborators/co-investigators have that supports the feasibility and/or safety of this study.

It is not necessary to summarize all discussion that has led to the development of the study protocol. The IRB is interested only in short summaries about experiences or preliminary work that suggest the study is feasible and that risks are reasonable relative to the benefits. Examples: Your team has already conducted a Phase 1 study of an experimental drug which supports the Phase 2 study being proposed in this application; your team has already done a small pilot study showing that the reading skills intervention described in this application is feasible in an after-school program with classroom aides; your team has experience with the type of surgery that is required to implant the study device; the study coordinator is experienced in working with subjects who have significant cognitive impairment.

This proposal builds on the study team's prior studies seeking to understand asthma management challenges faced by school-age children and their parents. We have also developed and tested other technology-based behavioral interventions in this population.

Our previous work sought to understand asthma management challenges from the perspective of parents and children (7-11 years). Three challenges emerged: 1) symptom monitoring, 2) medication use and tracking, and 3) shared asthma management responsibilities. Using a Human-Centered Design (HCD) framework, we collaborated with parent-child dyads to co-design Improving Asthma Care Together (IMPACT), a tailored shared management mobile health (mHealth) application that pairs the parent and child together as a shared management team. IMPACT helps families tailor asthma management strategies to fit the realities of their social environments while facilitating intentional transition of asthma management to the child. In other words, IMPACT was designed by the end-users, which suggests a high likelihood of feasibility and acceptability for study subjects.

Strengths of this study include: 1) prior successful recruitment of children with asthma and their parents; 2) established interdisciplinary study team with complimentary areas of expertise in asthma, spirometry, family informatics, and dyadic intervention expertise; 3) building logically on our prior work; 4) co-designing our intervention alongside parents and children that will use it; and 5) extensive usability testing during intervention development (prior IRB).

1.9 Supplements. Check all boxes that apply, to identify relevant Supplements that should be completed and uploaded to **Zipline**.

This section is here instead of at the end of the form to reduce the risk of duplicating information in this IRB Protocol form that you will need to provide in these Supplements.

Check all That Apply	Type of Research	Supplement Name
	Department of Defense The research involves Department of Defense funding, facilities, data, or personnel.	SUPPLEMENT Department of Defense
	Department of Energy The research involves Department of Energy funding, facilities, data, or personnel.	SUPPLEMENT Department of Energy
	Drug, biologic, botanical, supplement Procedures involve the use of any drug, biologic, botanical or supplement, even if the item is not the focus of the proposed research	SUPPLEMENT Drugs

	Emergency exception to informed consent Research that requires this special consent waiver for research involving more than minimal risk	SUPPLEMENT Exception from Informed Consent for Emergency Research (EFIC)
	Genomic data sharing Genomic data are being collected and will be deposited in an external database (such as the NIH dbGaP database) for sharing with other researchers, and the UW is being asked to provide the required certification or to ensure that the consent forms can be certified	SUPPLEMENT Genomic Data Sharing
	Medical device Procedures involve the use of any medical device, even if the device is not the focus of the proposed research, except when the device is FDA-approved and is being used through a clinical facility in the manner for which it is approved	SUPPLEMENT Devices
	Multi-site or collaborative study The UW IRB is being asked to review on behalf of one or more non-UW institutions in a multi-site or collaborative study.	SUPPLEMENT Multi-site or Collaborative Research
	Non-UW Individual Investigators The UW IRB is being asked to review on behalf of one or more non-UW individuals who are not affiliated with another organization for the purpose of the research.	SUPPLEMENT Non-UW Individual Investigators
	Other REDCap Installation Attestation for Electronic Consent The research will use a non-UW installation of REDCap for conducting and/or documenting informed consent.	SUPPLEMENT Other REDCap Installation
	None of the above	

1.10 **Confirm by checking the box below** that you will comply with these basic COVID infection and risk control measures, OR that you have an exception granted by the HSD Director: (a) the only in-person interactions are essential for the study; (b) study team members and participants will wear face coverings throughout all procedures; (c) all study staff and participants will be screened for COVID-19 just prior to each research visit; and (d) no participants over the age of 85 years will be enrolled if their in-person participation is not connected with a clinical visit. See this [webpage](#) for details, including what “screening” means.

Review the [HSD website](#) for current guidelines about which in-person research activities are allowable.

Confirmed

2 PARTICIPANTS

2.1 Participants. Describe the general characteristics of the subject populations or groups, including age range, gender, health status, and any other relevant characteristics.

60 children, ages 7-11 years, with persistent asthma and one parent will be recruited for this study. Participants will need to live in King, Pierce, or Snohomish County in Washington State.

Every effort will be made to recruit racial and ethnic minorities; asthma affects all races and ethnicities, with boys and non-Hispanic black children experiencing the highest prevalence. To ensure inclusion of racial and ethnic

minority participants, advertising will particularly target diverse population areas as identified by census tract data.

2.2 Inclusion and exclusion criteria.

a. **Inclusion criteria.** Describe the specific criteria that will be used to decide who will be included in the research from among interested or potential subjects. Define any technical terms in lay language.

Parent/Caregiver Inclusion Criteria

Child's primary caregiver residing with the child (50% or more); ≥ 18 years; speaks and reads English; has a smartphone with data plan; and has a parent-reported asthma responsibility mean score ≤ 2.5 (parent assumes the majority of asthma management responsibility). Participants seeking in person visits must reside within King, Pierce, and Snohomish Counties in Washington State, remote visits will be offered outside of those areas.

Child Inclusion Criteria

1) aged 7-11 years, 2) diagnosis of persistent asthma, defined as a prescription for a daily asthma medication; 3) speak English.

b. **Exclusion criteria.** Describe the specific criteria that will be used to decide who will be excluded from the research from subjects who meet the inclusion criteria listed above. Define any technical terms in lay language.

Parent/Caregiver Exclusion Criteria

None.

Child Exclusion Criteria

Parent report of conditions that impair the child's ability to learn shared-management including: 1) developmental delay (e.g., language < 5 -year level), 2) co-morbid condition (cancer, diabetes, autism); or 3) current asthma exacerbation at the time of recruitment (defined as a prescription for oral corticosteroids) as this is a serious health event and not an opportune time for learning shared management.

2.3 Prisoners.

IRB approval is required in order to include prisoners in research, even when prisoners are not an intended target population.

Is the research likely to have subjects who become prisoners while participating in the study?

For example, a longitudinal study of youth with drug problems is likely to have subjects who will be prisoners at some point during the study.

	No
	Yes

→ If yes, if a subject becomes a prisoner while participating in the study, will any study procedures and/or data collection related to the subject be continued while the subject is a prisoner?

No
Yes → If yes, describe the procedures and/or data collection that will continue with prisoner subjects

2.4 Will the proposed research recruit or obtain data from individuals that are known to be prisoners?

For records reviews: if the records do not indicate prisoner status and prisoners are not a target population, select "No". See the [GUIDANCE Prisoners](#) for the definition of "prisoner", which is not necessarily tied to the type of facility in which a person is residing.

	No
-------------------------------------	----

Document Date & Version

04/29/2021

Version 3.3

Researcher Date & Version

08/16/2021

Version 1.2

Yes → If yes, answer the following questions (i – iv).

i. Describe the type of prisoners, and their location(s):

ii. One concern about prisoner research is whether the effect of participation on prisoners' general living conditions, medical care, quality of food, amenities, and/or opportunity for earnings in prison will be so great that it will make it difficult for prisoners to adequately consider the research risks. How will the chances of this be reduced?

iii. Describe what will be done to make sure that (a) recruitment and subject selection procedures will be fair to all eligible prisoners and (b) prison authorities or other prisoners will not be able to arbitrarily prevent or require particular prisoners from participating.

iv. If the research is funded by one of these federal departments and agencies (Health & Human Services; Energy; Defense; Homeland Security; CIA; Social Security Administration), and/or will involve prisoners in federal facilities or in state/local facilities outside of Washington State: check the box below to provide assurance that study team members will (a) not encourage or facilitate the use of a prisoner's participation in the research to influence parole or pardon decisions, and (b) clearly inform each prisoner in advance (for example, in a consent form) that participation in the research will have no effect on his or her parole or pardon.

Confirmed

2.5 Protected populations. IRB approval is required for the use of the subject populations listed here. Check the boxes for any of these populations that will be purposefully included. (In other words, being a part of the population is an inclusion criterion for the study.)

The WORKSHEETS describe the criteria for approval but do not need to be completed and should not be submitted.

Population	Worksheet
 Fetuses in utero	WORKSHEET Pregnant Women
 Neonates of uncertain viability	WORKSHEET Neonates
 Non-viable neonates	WORKSHEET Neonates
 Pregnant women	WORKSHEET Pregnant Women

a. If you check any of the boxes above, use this space to provide any information that may be relevant for the IRB to consider.

2.6 Native Americans or non-U.S. indigenous populations. Will Native American or non-U.S. indigenous populations be actively recruited through a tribe, tribe-focused organization, or similar community-based organization?

Indigenous people are defined in international or national legislation as having a set of specific rights based on their historical ties to a particular territory and their cultural or historical distinctiveness from other populations that are often politically dominant.

Examples: a reservation school or health clinic; recruiting during a tribal community gathering

	No
	Yes

→ If yes, name the tribe, tribal-focused organization, or similar community-based organization. The UW IRB expects that tribal/indigenous approval will be obtained before beginning the research. This may or may not involve approval from a tribal IRB. The study team and any collaborators/investigators are also responsible for identifying any tribal laws that may affect the research.

2.7 Third party subjects. Will the research collect private identifiable information about *other individuals* from the study subjects? Common examples include: collecting medical history information or contact information about family members, friends, co-workers.

"Identifiable" means any direct or indirect identifier that, alone or in combination, would allow you or another member of the research team to readily identify the person. For example, suppose that the research is about immigration history. If subjects are asked questions about their grandparents but are not asked for names or other information that would allow easy identification of the grandparents, then private identifiable information is not being collected about the grandparents and the grandparents are not subjects.

	No
	Yes

→ If yes, these individuals are considered human subjects in the study. Describe them and what data will be collected about them.

2.8 Number of subjects. Is it possible to predict or describe the maximum number of subjects (or subject units) needed to complete the study, for each subject group?

Subject units mean units within a group. For most research studies, a group will consist of individuals. However, the unit of interest in some research is not the individual. Examples:

- Dyads such as caregiver-and-Alzheimer's patient, or parent and child
- Families
- Other units, such as student-parent-teacher

Subject group means categories of subjects that are meaningful for the specific study. Some research has only one subject group – for example, all UW students taking Introductory Psychology. Some common ways in which subjects are grouped include:

- By intervention – for example, an intervention group and a control group.
- By subject population or setting – for example, urban versus rural families
- By age – for example, children who are 6, 10, or 14 years old.

The IRB reviews the number of subjects in the context of risks and benefits. Unless otherwise specified, if the IRB determines that the research involves no more than minimal risk: there are no restrictions on the total number of subjects that may be enrolled. If the research involves more than minimal risk: The number of enrolled subjects must be limited to the number described in this application. If it is necessary later to increase the number of subjects, submit a Modification. Exceeding the IRB-approved number ([over-enrollment](#)) will be considered non-compliance.

No → If no, provide the rationale in the box below. Also, provide any other available information about the scope/size of the research. You do not need to complete the table.

Example: It may not be possible to predict the number of subjects who will complete an online survey advertised through Craigslist, but you can state that the survey will be posted for two weeks and the number who respond is the number who will be in the study.

Yes → If yes, for each subject group, use the table below to provide the estimate of the maximum desired number of individuals (or other subject unit, such as families) who will complete the research.

Group name/description	Maximum desired number of individuals (or other subject unit, such as families) who will complete the research
Provide numbers for the site(s) reviewed by the UW IRB and for the study-wide total number; example: 20/100	
Children with asthma	65 (to account for anticipated attrition)
Parents of child with asthma	65 (to account for anticipated attrition)
<hr/> <hr/> <hr/>	

2.9 COVID-19 Screening. If there will be any in-person interactions with the subjects, describe how you will screen them for COVID-19 symptoms within the 24 hours before the interaction. Also, describe the COVID-19 screening procedures for the study staff who will interact with the subjects.

Acceptable procedures include some type of symptom check or attestation, or a SARS-CoV-2 test with quick access to results. Symptom attestation involves an individual reviewing a list of symptoms and declaring the presence or absence of those symptoms. HSD strongly encourages adapting this Washington State Department of Health Screening Tool <https://www.doh.wa.gov/Portals/1/Documents/1600/coronavirus/Employervisitor screening guidance.pdf> or the UW EH&S Example Symptom Self-Attestation in this document: <https://www.ehs.washington.edu/system/files/resources/guidance-symptom-monitoring-COVID-19.pdf>. If you will test for the virus, you must also describe here whether the testing lab is CLIA-certified and how the results will be reported to the subjects.

At this time, we anticipate offering in-person sessions. For in-person sessions, we will complete a symptom attestation using the WA DOH questions. Attestation will be sent to study subject parents via REDCap SMS message or email (whatever participants prefer) 24 hours before their study visit.

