Title: Improving Asthma Care Together (IMPACT): A Shared Management Pilot Study

NCT #: NCT04908384

Document Date: 03/19/2020

Statistical Analysis Plan

Data Analysis.

Feasibility. Eligibility, enrollment, and retention (number who complete study) data will be summarized in a study flowchart. A priori feasibility benchmarks include $\geq 60\%$ recruitment (eligible dyads who enroll) and $\geq 80\%$ retention; these benchmarks are based on our previous research (80% recruitment, 86% retention) and similar studies.¹⁰⁶⁻¹¹¹ Study withdrawal reasons and timing will also be reported.

Acceptability. Participants will rate IMPACT acceptability via Acceptability of Intervention (AIM) survey and semi-structured interview. The a priori acceptability benchmark will be $\geq 60\%$ of participants rating IMPACT as acceptable (4 or 5 on AIM, table 3).^{106-108,111} Additional participant acceptability feedback will be documented via an exit interview. Quantitative data will be summarized using descriptive statistics whereas qualitative data will undergo thematic analysis, described above.

Analysis of the primary outcomes (asthma responsibility score, self-efficacy). Descriptive summaries of de-identified data will be transferred into SPSS 24 (IBM Corp, Armonk, NY) for analyses. Distributions of interval and ratio level variables will be checked for normality and transformed as necessary. We will compare characteristics of those who completed the study to those who did not to inform the generalizability of findings. We expect an increase in asthma management responsibility scores and increased dyadic interdependence (i.e. nonindependence of scores between dyads)¹⁰³ between parent and child-reported outcomes over time in the intervention group, suggesting true shared management.

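### Does the entry of 65 dyads for attrition conflict with the planned sample of 60 and the team's own 86% retention?

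*Protocol*

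**What the plan says.** Protocol section 1.5 describes a sample of sixty children, each with a parent, and aim 1 is to determine "feasibility, acceptability and initial efficacy of IMPACT with 60 parent-child dyads". Section 2.1 repeats the number: "60 children, ages 7-11 years, with persistent asthma and one parent will be recruited for this study".

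Section 2.8 is a form table. Its instruction asks for the "maximum desired number of individuals (or other subject unit, such as families) who will complete the research". The team's entry is "65 (to account for anticipated attrition", once for children and once for parents. The same section says that, for research judged to be no more than minimal risk, "there are no restrictions on the total number of subjects that may be enrolled". Section 1.8a states: "This is a minimal risk study that involves a clinical trial".

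The SAP gives no sample size. Under Feasibility it sets floors of 60% for recruitment and 80% for retention and adds that "these benchmarks are based on our previous research (80% recruitment, 86% retention" and on similar studies. It treats retention as the number completing: "Eligibility, enrollment, and retention (number who complete study) data will be summarized in a study flowchart".

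**The concern.** Two numbers appear for one trial, and neither is labelled as randomised or completing. The note beside the 65 reads like a planning statement: enrol five more than needed so that enough remain. On that reading the allowance is 5 dyads in 65, or 7.7%, while the team's reported experience is a 14% loss and its own benchmark tolerates 20%. The trial would then finish with fewer than 60 dyads, and the preliminary effect sizes in aim 1c would be less precise than a reader might suppose.

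It is also awkward that the attrition note sits under a heading about completers. Taken literally, more dyads would complete (65) than are recruited (60). In a pilot where retention is itself a feasibility measure, one expects the planned numbers to agree with the retention history.

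**Working it through.** **Inputs**

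- 60 dyads: Protocol 1.5 and 2.1.
- 65 children and 65 parents: Protocol 2.8.
- 86% previous retention and a floor of 80%: SAP, Feasibility.
- Not given in either document: an attrition rate for this trial, a completer target, a power calculation or an allocation ratio.

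**Can the 65 be reproduced?** Enrolment needed = completers / retention. With 60 as a completer target (an assumption):

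- 60 / 0.86 = 69.8, so 70 dyads.
- 60 / 0.80 = 75 dyads.
- Retention at which 65 would be right: 60 / 65 = 0.923.

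Neither documented rate gives 65. But neither is offered as its basis, so this does not show a stated calculation to be wrong.

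**The three readings**

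1. *65 enrolled, 60 meant to complete.* Expected completers are 65 × 0.86 = 55.9, or 65 × 0.80 = 52.0. The shortfall against 60 is about 4 to 8 dyads.
2. *65 completing, as the form's heading literally asks.* Enrolment would have to be 65 / 0.86 = 75.6 (76) or 65 / 0.80 = 81.25 (82), which contradicts the 60 in section 2.1.
3. *60 recruited, with 65 as a ceiling.* Expected completers are 60 × 0.86 = 51.6, or 60 × 0.80 = 48.0. This agrees with sections 1.5 and 2.1 and with the form's request for a maximum. It leaves only the reason for the extra five loosely explained.

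**Effect on precision.** Take equal arms, completers only and no baseline adjustment (all assumptions). The approximate 95% half-width of a standardised mean difference is 1.96 × √(4/N), where N is the total number of dyads analysed:

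| N analysed | Half-width (SD) |
|---|---|
| 60 | 0.506 |
| 56 | 0.524 |
| 52 | 0.544 |
| 48 | 0.566 |

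From 60 to 48 the interval widens by 0.566 / 0.506 = 1.12, or about 12%. Between readings 1 and 3 at the same retention the gap is about 0.02 SD: 0.524 against 0.544 at 86%, and 0.544 against 0.566 at 80%.

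**Effect on the feasibility criteria.** Both benchmarks are proportions. The retention floor is met with 48 of 60 or with 52 of 65. Recruitment is the share of eligible dyads who enrol. Neither threshold changes with the enrolment number.

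**The case for a change.** The strongest opposing case is that the team itself wrote that the 65 allows for attrition. That is more than a template phrase, and no reading reconciles every statement. Feasibility is part of aim 1, so a protocol that measures retention ought to say what retention it assumed. The remedy would be a few words and no extra dyads. If 60 completers were wanted, the binomial chance of getting them from 65 independent dyads is only about 9% at 86% retention and 0.6% at 80%.

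Part of this stands: the wording is inconsistent, and a careful author would have labelled the two numbers. The rest is weaker. The probabilities answer whether 60 will complete, which the protocol does not ask. They also treat 86% as a known rate, although the size of the earlier study is not given; at 90% retention the 9% becomes 36%. The comparison of 92.3% with 86% has the same weakness, because it needs a completer target that the documents do not set and that section 2.1 points away from.

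A planned 60 under a maximum of 65 is not in itself a contradiction. Nor does the 65 act as a binding cap if the ethics board accepts the team's minimal-risk description; if it does not, 60 still lies within the 65.

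**Conclusion.** There is a small inconsistency of wording, and no change to the plan is needed. The most natural reading is that 60 dyads are to be recruited, with a few more permitted. Analysts would report the numbers screened, enrolled and completing in the flowchart that the SAP already plans, and would calculate retention from those counts.

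Whether 60 or 65 dyads enter, the feasibility thresholds and the planned analyses are unchanged. The half-width stays between 0.51 and 0.57 SD over the scenarios of 60 to 48 dyads analysed. Those figures assume equal allocation and completers only. They may overstate the loss, because the SAP plans baseline adjustment and uses full information maximum likelihood for the dyadic models, and Protocol section 10.8 lets participants who withdraw continue with follow-up assessments.

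A sentence naming the enrolment number and the attrition assumed would be tidier, but it would not alter the conduct of the trial or any conclusion from it. The judgement would differ only if the trial had a power-based completer target that 65 was meant to secure, and the documents show none.
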